6.3.2.2. Self Monitoring of Plasma Glucose

All subjects should be instructed to measure and record plasma glucose values from their glucose meter at least 4 times a day at the suggested times for at least 2 consecutive days in the week before any study center/telephone contact

- Before breakfast
- Before lunch
- Before dinner
- At bedtime

All results of self plasma glucose monitoring will be stored in the subject's glucose meter and communicated to the study site as directed by the investigator. The investigator will review the glucose meter readings at the study visit/telephone call and adjust insulin doses as per [Table 1](#) and [Table 2](#). If a measurement is only available for 1 day, this will be used to assess the need for insulin dose adjustment but the site will need to explain to the subject the importance of having at least 2 daily measurements. Additional glucose meter monitoring should be performed as per local practice.

Weekly telephone calls (if there is no scheduled study visit) must take place between the investigator and subject from Baseline to Week 16, as well as at Week 22, Week 34, Week 46, and as required until the end of the follow-up phase, in order to optimise insulin titration. It is recommended that the investigator calls the subjects every 3-5 days during the first 2 weeks of randomised therapy and after Week 6 when the study drug dose is increased.

NOTE: the use of a GLP-1R agonist (albiglutide) is expected to decrease the need for insulin and, therefore, the investigator will need to ensure careful follow-up of each subject accordingly, particularly in the first two weeks after randomisation.

6.3.2.3. 7-Point Self-Monitored Plasma Glucose Profile

A 7 point glucose profile will be conducted at the times specified in the Time and Events Table ([Table 3](#)). Subjects should be instructed to measure and record plasma glucose values from their glucose meter at the following times:

- Before breakfast (at least 8 hours without food intake)
- 2 hours after breakfast
- Before lunch
- 2 hours after lunch
- Before dinner
- 2 hours after dinner
- At bedtime

6.3.2.4. 72-hour Continuous Glucose Monitoring

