Continuous glucose monitoring (CGM) will be conducted at the times specified in the Time and Events Table ([Table 3](#)). Three days before the visit, the subject should make an additional visit to the study site to have the continuous glucose monitor fitted/inserted. It should be worn for 3 consecutive days and be removed at the scheduled study visit. Whilst wearing the CGM, subjects should continue to monitor their plasma glucose as described in Section [6.3.2.2](#) and on one of the days, conduct the 7-point glucose profile as described in Section [6.3.2.3](#).

Subjects and their physicians will not have access to the CGM data during the period of monitoring.

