
Subject-Reported Hypoglycaemic Events:
 
 • For the time periods (Baseline to Week 24; $>$Week 24 \leqWeek 52): the average number of significant events per subject (i.e. number of subject-reported events divided by the number of subjects); percentage of subjects reporting significant events; and the total number of significant events; will be presented for each treatment group. • Data will be listed.

7-point glucose profile:
 
 • The glucose level at each of the 7 specified timepoints of the 7-point glucose profile will be summarised for each treatment group using descriptive summary statistics. • The number and percentage of subjects with any hypoglycaemic excursions will be presented for each treatment group. • The number of hypoglycaemic excursions that each subject experienced will be summarised for each treatment group using descriptive summary statistics. • The greatest magnitude of hypoglycaemic excursion of each subject will be summarised for each treatment group using descriptive summary statistics • The summaries will be repeated for hyperglycaemic excursions. • Data will be listed.
Endpoint(s)

 • Proportion of time spent with plasma glucose ≤ 3.9 mmol/L; between >3.9 and 10.0 mmol/L; and >10.0 mmol/L (72h CGM) at Baseline, Week 28 and Week 52.

Secondary Statistical Analyses	
Model Specification	

 Change from baseline in time spent (h/day) with plasma glucose ≤ 3.9 mmol/L at Week 28 and Week 52; Change from baseline in time spent (h/day) with plasma glucose between >3.9 and 10.0 mmol/L at Week 28 and Week 52; Change from baseline in time spent (h/day) with plasma glucose >10.0 mmol/L at Week 28 and Week 52; Statistical analysis will be performed separately for the 3 endpoints, however care should be taken when interpreting results as due to the nature of the endpoints the data is linked. The endpoints will be statistically analysed using separate mixed models repeated measures (MMRM) models, using PROC MIXED in SAS. The analysis will be performed as described for the secondary endpoints using the MMRM methodology. 	
Model Checking & Diagnostics	

 Refer to Appendix 9: Model Checking and Diagnostics for Statistical Analyses. Due to the correlation between the 3 endpoints, a multivariate (MANOVA) approach may additionally be explored. 	
Model Results Presentation	

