
 Data from the 7-point blood glucose profile page in the eCRF will be used for this endpoint. Data recorded from the glucose meter to the electronic diary will not be used. The schedules collection times for the 7-point glucose profile are: before breakfast (at least 8 hours without food intake); 2 hours after breakfast; before lunch; 2 hours after lunch; before dinner; 2 hours after dinner; at bedtime. Glucose will be presented in mmol/L. A glucose value reported in mg/dL will be converted to mmol/L by multiplying the value by 0.05551. The 7-point glucose profile will be assessed at Baseline, Week 28 and Week 52. All non-missing data will be included in the summaries of glucose levels at each of the 7 specified time-points (before breakfast, 2 h after breakfast, etc.). To be evaluable for the endpoints relating to number and magnitude of hypo/hyperglycaemic excursions (endpoints detailed below) the following rules will apply: 
 A subject with non-missing glucose values for at least 4 of the 7 scheduled time-points will be evaluable for hypoglycaemic excursions and hyperglycaemic excursions A subject with <4 non-missing glucose values will be evaluable for hypoglycaemic excursions only if one or more of the non-missing glucose values is a hypoglycaemic excursion (i.e., blood glucose level is ≤3.9 mmol/L) A subject with <4 non-missing glucose values will be evaluable for hyperglycaemic excursions only if one or more of the non-missing glucose values is a hyperglycaemic excursion (i.e., blood glucose level is >10.0 mmol/L) Subjects will be determined as evaluable for hypoglycaemic excursions and hyperglycaemic excursions separately at each visit, based on the non-missing data reported at that visit. At Baseline, Week 28 and Week 52, the following parameters will be calculated for each subject: 
 Hypoglycaemic Excursions: A hypoglycaemic excursion is defined as an occurrence where the blood glucose level is ≤3.9 mmol/L (i.e. ≤70 mg/dL) Any hypoglycaemic excursions (yes/no) Number of hypoglycaemic excursions (e.g. expected 0 -7) Greatest hypoglycaemic excursion: this will be calculated as 3.9 mmol/L minus the lowest recorded glucose level during the 7-point glucose profile. If a subject has data recorded in the interval, but does not have a value ≤3.9 mmol/L, the subject's greatest hypoglycaemic excursion for that interval would be 0 mmol/L. Hyperglycaemic Excursions: A hyperglycaemic excursion is defined as an occurrence where the blood glucose level is >10.0 mmol/L (i.e. >180 mg/dL) Any hyperglycaemic excursions (yes/no) Number of hyperglycaemic excursions (e.g. expected 0 -7) Greatest hyperglycaemic excursion: this will be calculated as the largest recorded glucose level during the 7-point glucose profile minus 10.0 mmol/L. If a subject has data recorded in the

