
Other Efficacy Endpoints	
	interval, but does not have a value $>10.0 \text{ mmol/L}$, the subject's greatest hyperglycaemic excursion for that interval would be 0 mmol/L.
72 hour CGM	

 Glucose variability is also assessed using continuous glucose monitoring (CGM), where glucose is sampled every 5 mins for 72 hours. 72-hour CGM will be performed at baseline, week 28 and week 52. At each time point the following parameters will be calculated for each subject: 
 Time spent with a plasma glucose $\leq 3.9 \text{ mmol/L}$ Time spent with a plasma glucose between >3.9 and 10.0 mmol/L Time spent with a plasma glucose $>10.0 \text{ mmol/L}$ Data will be derived as follows: A subject must have at least 24 hours of CGM data recorded in order to be considered evaluable (note, this does not need to be in one continuous period) If a value of x is recorded at time 0, a value of y at time 5 mins, and a value of z at time 10 mins then a subject will be considered to have a plasma glucose level of x from time 0-5 (5mins); a value of y from time 5-10 (5mins); a value of z from time 10-15 (5mins); etc. Each 5 minute time period will be assigned to time spent $\leq 3.9 \text{ mmol/L}$, between >3.9 and 10.0 mmol/L and $>10.0 \text{ mmol/L}$. Data for each subject will be summed into the 3 categories, over the time period they have available, so they have: 
 Actual time spent $\leq 3.9 \text{ mmol/L}$, Actual time spent between >3.9 and 10.0 mmol/L Actual time spent $>10.0 \text{ mmol/L}$. Total actual time To calculate the actual time spent within each range, each CGM observation will be assigned as $\leq 3.9 \text{ mmol/L}$, between >3.9 and 10.0 mmol/L, and $>10.0 \text{ mmol/L}$. The number of observations within each range will be summed, and the total number of observations within each range will be multiplied by 5 minutes to calculate the actual time within each range. The total actual time is the sum of the actual time spent within each range for the 3 ranges. There may be periods of missing data within the 72h CGM. As it is unknown what the plasma glucose value was during these times, they will be excluded from calculations. 	
For each category, data will be converted into time spent for a 24 hour period as follows:	

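### Excursion counts from the 7-point glucose profile are not scaled to the number of readings, so from 4 of 7 readings upward a missing slot scores as no excursion

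*SAP*

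**What the plan says.** The number and magnitude of hypo- and hyperglycaemic excursions from the 7-point profile at Baseline, Week 28 and Week 52 form a secondary endpoint for glycaemic variability (Protocol 6.3.1.2; SAP 2.2).

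SAP 11.5.4 sets the derivation:
- **Source.** Only the 7-point page of the eCRF counts: "Data recorded from the glucose meter to the electronic diary will not be used".
- **Schedule.** Before breakfast, then "2 hours after breakfast; before lunch; 2 hours after lunch; before dinner; 2 hours after dinner; at bedtime".
- **Evaluability.** "A subject with non-missing glucose values for at least 4 of the 7 scheduled time-points will be evaluable for hypoglycaemic excursions and hyperglycaemic excursions". Below four readings, a subject is evaluable for an excursion type only if one of the recorded values is such an excursion.
- **Outputs per subject and visit.** Any excursion (yes/no), the number of excursions on a 0 to 7 scale, and the greatest magnitude, set to 0 mmol/L when no recorded value crosses the threshold.

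SAP 8.1.2 then reports: "The number of hypoglycaemic excursions that each subject experienced will be summarised for each treatment group using descriptive summary statistics". The same is done for hyperglycaemic excursions. No formal treatment comparison is planned.

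Routine self-monitoring (Protocol 6.3.2.2) asks for readings "at least 4 times a day at the suggested times for at least 2 consecutive days in the week before any study center/telephone contact". The suggested times are before each of the three meals and at bedtime.

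**The concern.** From four readings upward, the subject-level count depends on how many slots were filled as well as on glucose. A subject with four readings has four chances to show an excursion and is averaged with subjects who had seven, with nothing in the derivation to allow for the difference. The any-excursion flag and the zero magnitude behave the same way.

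The rule also ignores which slots are filled. The four non-post-meal slots are the routine self-monitoring times, so the three 2-hour post-meal readings are the extra work the profile asks for. They are also where Protocol 1.2 expects the drug class to act, through smaller postprandial excursions. A difference in post-meal completeness between arms, or between Baseline and Week 52, could therefore look like a difference in hyperglycaemic excursions.

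The SAP takes more care elsewhere. In the CGM derivation, gaps are handled thus: "As it is unknown what the plasma glucose value was during these times, they will be excluded from calculations", and time in range is divided by observed time. For meal-time insulin, a day enters the average only if breakfast, lunch and dinner doses are all non-missing.

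**Working it through.** **Inputs from the documents.** Seven slots, an evaluability threshold of four, and an unscaled count (SAP 11.5.4); four routine times (Protocol 6.3.2.2). The plan gives no slot-level excursion risks and no expected completeness, so any risks used below are assumptions. There is no planned numerical result to reproduce.

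**Step 1: which slots the threshold protects.** Seven slots minus the four routine times leaves exactly the three post-meal slots. There are 35 ways to choose 4 of 7 slots: 1 has no post-meal reading, 12 have one, 18 have two and 4 have all three. All 35 are evaluable. A count threshold alone guarantees 0 post-meal readings at 4 of 7, 1 at 5, 2 at 6 and 3 at 7. These are counts of patterns; they say nothing about how often each would occur.

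**Step 2: equal slot risks.** If every slot has risk p, a full profile expects 7p excursions and a profile with k readings expects kp. The relative error is k/7 - 1:
- k = 6: 6/7 - 1 = -14%
- k = 5: 5/7 - 1 = -29%
- k = 4: 4/7 - 1 = -43%

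This applies to hypo- and hyperglycaemic counts alike and does not depend on p.

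**Step 3: post-meal slots missing, hyperglycaemia only.** Let a be the risk of a value above 10.0 mmol/L at each pre-meal or bedtime slot, and b the risk at each post-meal slot. A full profile expects 4a + 3b; the four non-post-meal slots alone expect 4a. The proportion lost is 3b/(4a + 3b). For assumed a and b:

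| a | b = 0.20 | b = 0.35 | b = 0.50 |
|---|---|---|---|
| 0.1 | 60% | 72% | 79% |
| 0.2 | 43% | 57% | 65% |
| 0.3 | 33% | 47% | 56% |

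At the extremes of loss, a = 0.3 and b = 0.2 gives 1.8 falling to 1.2, and a = 0.1 and b = 0.5 gives 1.9 falling to 0.4. If slots are also independent, the probability of any excursion is 1 - (1-a)^4 (1-b)^3 for a full profile and 1 - (1-a)^4 for the four slots. At a = 0.1, b = 0.2 it falls from 0.66 to 0.34; at a = 0.3, b = 0.5, from 0.97 to 0.76.

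**Step 4: arm level.** If a share s of evaluable subjects has only those four slots and the rest are complete, the arm mean is low by s times the loss in Step 3. With s assumed to be 20%, that is 0.20 x 33% = 7% to 0.20 x 79% = 16%. The documents give no value for s. The calculation also leaves out subjects with fewer than four readings, who enter only when they show an excursion and so raise the same summaries. The net direction cannot be derived.

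**The case against.** A reader might infer that ordinary four-times-a-day meter readings are enough to make a subject evaluable. The documents do not support that. SAP 11.5.4 takes data only from the 7-point eCRF page and excludes meter-to-diary data, and SAP 11.5.3 identifies routine and 7-point readings by separate codes. A blank 7-point page is not evaluable, however many routine readings exist. The extreme case needs exactly those four values to be entered on that page. Nothing in the documents shows that this is common.

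A reader might also infer that excursion counts must fall as compliance falls. That does not follow either, because the rule for fewer than four readings works in the opposite direction.

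The plan has partial safeguards. Table 2.23 summarises glucose at each of the seven time-points from all non-missing data, and Protocol 8.3.5.1 calls for numbers of available and missing observations, so uneven post-meal completeness should be visible. CGM is worn over the day of the profile and time above 10.0 mmol/L is modelled. No test is attached to the excursion endpoint, and the SAP records that the company is not developing the drug for type 1 diabetes.

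These arguments limit the stakes but do not remove the defect. Table 2.23 gives glucose levels, not excursion frequency, and does not adjust Tables 2.24 to 2.29. Protocol 3.2 keeps the 7-point profile because CGM is not fully validated and can fail technically, so CGM cannot stand in for a sound derivation here.

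**Conclusion.** The point stands as a minor one. For evaluable profiles with four to six readings, the derivation treats unmeasured slots as free of excursions. The understatement per subject is 14%, 29% or 43% with 6, 5 or 4 readings if slot risks are equal. For hyperglycaemia it is about 33-79% if only the four non-post-meal slots are on the page, over the assumed risks. The first set of figures follows from the rule plus equal risks; the second rests wholly on assumed risks.

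The bias in an arm mean or a treatment contrast is unknown in size and sign. The post-meal argument applies to hyperglycaemic excursions; for hypoglycaemia only the general scaling problem has been shown. The documents do not establish that any particular minimum number of post-meal readings is the right evaluability rule. The primary analysis is not affected.

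**What to change.** In SAP 11.5.4 and 8.1.2, and in Tables 2.24, 2.25, 2.27 and 2.28, keep the planned subject-level summaries and add, by arm and visit:
1. The proportion of non-missing readings in excursion at each of the seven slots, with the number of readings behind it.
2. The sum of the seven slot proportions, as the expected count per 7-point profile.

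Use all non-missing readings, as Table 2.23 does, so that neither the four-reading threshold nor the exception below it affects these figures. They still assume that, within slot, arm and visit, missing readings resemble observed ones.

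As an optional sensitivity summary, repeat the subject-level hyperglycaemia results (Tables 2.27 to 2.29) in subjects with all three post-meal readings, or with a minimum number stated in advance.

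The cost is SAP wording and a little extra table work. No new data are needed, and no subject leaves the planned summaries.

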11.5.5. Exploratory Endpoints

Exploratory Endpoints

Urinary C-peptide 120 minutes after a mixed meal (urinary creatinine corrected)
 
 Urinary C-peptide from the MMTT will be corrected for urinary creatinine and will be provided in the data as the urinary C-peptide creatinine ratio parameter. No derivation necessary. The protocol statistical section refers to this variable as 120 minutes urinary C-peptide AUC, however for consistency with how the parameter is calculated it will be referred to as the urinary C-peptide creatinine ratio.

Audit of Diabetes Dependent Quality of Life (ADDQoL)
 
 The ADDQoL is a validated instrument for the assessment of the impact of diabetes on quality of life. The ADDQoL 19 will be used in this trial. The ADDQoL consists of two overview items designed for audit purposes: 
 generic 'Present QoL' diabetes-specific 'Impact of diabetes on QoL' These two overview items will be scored individually. The general overview item is measured on a 7-point scale where -3 represents extremely bad and +3 represents excellent (e.g., from -3 to +3). The diabetes-specific overview item is measured on a 5-point scale of -3 (maximum negative impact of diabetes) to + 1 (maximum positive impact of diabetes). A further 19 items assess the impact of diabetes on a range of quality of life domains: 
 Leisure activities Working life Journeys Holidays Physical health Family life Friendships and social life Personal relationship Sex life Physical appearance Self-confidence Motivation People's reactions Feelings about the future Financial situation Living conditions Dependence on others Freedom to eat Freedom to drink Respondents rate both impact of diabetes on applicable domains and also the importance of those domains for their QoL. Respondents also indicate if some domains are not relevant to them. The instrument thus yields a weighted global score calculated only on domains relevant

Exploratory Endpoints

- to the respondent, in addition to individual domain and overview item scores.
- All 19 questions are measured on a 5-point scale, ranging from -3 (greatest negative impact) to +1 (greatest positive impact).
- Subjects are also required to give an “importance score” rating for these 19 domains on a 4-point scale, from 0 (not at all important) to 3 (very important).
- The option of “non-applicable” is included in five of the domains (working life, holidays, family life, close personal relationship and sex life) if it is considered to be irrelevant by the subjects
- The weighted impact score is calculated by multiplying the importance scores and impact scores. The average weighted impact score is obtained by averaging all the weighted scores and is interpreted as the overall weighted impact score of DM on quality of life.

Scoring

- *Two overview items:* scored individually
- *Individual domains:* scores
 - Impact rating (score -3 to +1)
 - Importance rating (score 0 to 3)
- *Individual domains:* a weighted score for each domain is calculated as follows:
 - Weighted impact score=impact rating (score -3 to +1) x importance rating (score 0 to 3)
 - Score -9 (maximum negative impact of diabetes) to +3 (maximum positive impact of diabetes)
 - NB: ‘Unimportant’ domains score 0, regardless of magnitude of impact of diabetes. Domains with no impact of diabetes score 0, regardless of their importance to QoL. Any non-applicable domains are not scored.
- *Average weighted impact score:*
 - = sum of weighted ratings of applicable domains / N of applicable domains

Score -9 (maximum negative impact of diabetes) to +3 (maximum positive impact of diabetes)
- Although described here for completeness, weighted scores will not be derived, either overall or for individual domains. Only data as collected in the ADDQoL will be listed, with no further derivation.

11.5.6. Immunogenicity

Immunogenicity

- Immunogenicity was assessed at Baseline, Week 2, 4, 6, 8, 16, 28, 40, 52 and 64
- The following antibodies will be assessed:
 - Anti-albiglutide antibody
 - Anti-GLP-1 antibody
 - Anti-HA (Albumin) antibody
 - Anti-albiglutide neutralising antibody
- Note, only anti-albiglutide antibody positive samples will be analysed for the other antibodies
- Results will be assessed as positive or negative.
- [Note: the positive/negative result will be provided in the data, not derived by programming]
- For testing that includes confirmatory analyses, subjects are considered antibody positive if both the screening and confirmatory results were positive; antibody negative subjects are those with a negative screening result or a positive screening result but a negative confirmatory result. For testing that includes confirmatory analyses, subjects with a positive screening result, but no confirmatory result (i.e. test not done) will be considered unknown antibody status. For the anti-HA antibody, subjects are considered antibody positive or negative based on the screening result, since confirmatory testing is not performed. Results reported as "Not applicable" are not considered informative and are equivalent to missing for purposes of summaries and listing.
- In addition, anti-albiglutide positive samples will be titrated to obtain the titre of antibodies (anti-albiglutide antibody titre and anti-albiglutide neutralising antibody titre). These will be provided as numeric values (0 dps).
- Additionally, for subjects who experience systemic allergic reactions that include anaphylaxis, a sample will be taken at a time as close as possible to the event. The sample will be tested for albiglutide-specific IgE antibody, including the titre level. These results will not be summarised, but will be presented in data listings.
- Anti-albiglutide antibody positive subjects are defined as subjects with an anti-albiglutide antibody result of positive at any visit (including those with a positive result at baseline, regardless of whether they had a positive post-baseline result). Anti-albiglutide negative subjects are defined as those subjects with an anti-albiglutide antibody result of negative at all visits. The result derived from screening and confirmatory results (where applicable) will be used for this assessment.

